10.1.9 Publication Policy

The results of this study may be published or presented at scientific meetings.

The sponsor will comply with the requirements for publication of study results. In accordance with standard editorial and ethical practice, the sponsor will generally support publication of multicenter studies only in their entirety and not as individual site data. In this case, a coordinating Investigator will be designated by mutual agreement.

Authorship will be determined by mutual agreement and in line with International Committee of Medical Journal Editors authorship requirements.

This document cannot be used to support any marketing authorization application and any extensions or variations thereof.

PUBLIC COPY

10.2 Appendix 2: Clinical Laboratory Tests

- The tests detailed in the table below will be performed by the central laboratory.
- Local laboratory results are only required in the event that the central laboratory results are not available in time for either study treatment administration and/or response evaluation. If a local sample is required, it is important that the sample for central analysis is obtained at the same time. Additionally, if the local laboratory results are used to make either a study treatment decision or response evaluation, the results must be entered into the eCRF.
- Protocol-specific requirements for inclusion or exclusion of participants are detailed in Section 5.1 and Section 5.2 of the protocol.
- Additional tests may be performed at any time during the study as determined necessary by the Investigator or required by local regulations.

Protocol-Required Safety Laboratory Assessments

Laboratory Assessments	Parameters				
Hematology	Platelet Count	RBC Indices:		White blood cell count with Differential:	
	Red blood cell (RBC) count	Mean corpuscular volume		Neutrophils	
	Hemoglobin	Mean corpuscular hemoglobin		Lymphocytes	
	Hematocrit	%Reticulocytes		Monocytes Eosinophils Basophils	
Clinical Chemistry ^a	Blood Urea Nitrogen (BUN)	Potassium	Aspartate Aminotransferase (AST)/ Serum Glutamic-Oxaloacetic Transaminase (SGOT)	Total and direct bilirubin	
	Creatinine	Sodium	Alanine Aminotransferase (ALT)/ Serum Glutamic-Pyruvic Transaminase (SGPT)	Total Protein Albumin	
	Glucose (fasting state, preferred)	Calcium	Alkaline phosphatase		C-reactive protein (CRP)
	Lactate dehydrogenase (LDH)	High-density lipoprotein (HDL)	Total Cholesterol		Triglycerides
Routine Urinalysis	
 • Specific gravity 				

Laboratory Assessments	Parameters
	
 • pH, glucose, protein, blood, ketones, albumin, bilirubin, urobilinogen, nitrite, leukocyte esterase by dipstick • Microscopic examination (if blood or protein is abnormal)
Other Screening Tests	
 • Serum or urine human chorionic gonadotropin pregnancy test (as needed for women of childbearing potential)^b • PTT and INR tests • Serology testing (for Hepatitis B, Hepatitis C, and HIV) • All study-required laboratory assessments will be performed by a central laboratory. • The results of each test must be entered into the CRF.

NOTES :
 
^a Details of liver chemistry stopping criteria and required actions and follow-up assessments after liver stopping or monitoring event are given in Section 10.6 and Appendix 6. All events of ALT $\geq 3xULN$ and bilirubin $\geq 2xULN$ (>35% direct bilirubin) or ALT $\geq 3xULN$ and international normalized ratio (INR) >1.5, if INR measured, may indicate severe liver injury (possible Hy's Law) and must be reported as an SAE (excluding studies of hepatic impairment or cirrhosis).
 
^b Local urine testing will be standard for the protocol unless serum testing is required by local regulation or IRB/IEC.
	

Investigators must document their review of each laboratory safety report.

Laboratory/analyte results that could unblind the study will not be reported to investigative sites or other blinded personnel until the study has been unblinded.

10.3 Appendix 3: Adverse Events – Definitions and Procedures for Recording, Evaluating, Follow-up, and Reporting

10.3.1 Definition of AE

AE Definition

- An AE is any untoward medical occurrence in a patient or clinical study participant, temporally associated with the use of study medication, whether or not considered related to the study medication.
- NOTE: An AE can therefore be any unfavorable and unintended sign (including an abnormal laboratory finding), symptom, or disease (new or exacerbated) temporally associated with the use of study medication.

Events Meeting the AE Definition

- Any abnormal laboratory test results (hematology, clinical chemistry, or urinalysis) or other safety assessments (eg, ECG, radiological scans, vital signs measurements), including those that worsen from Baseline, considered clinically significant in the medical and scientific judgment of the Investigator (ie, not related to progression of underlying disease).
- Exacerbation of a chronic or intermittent pre-existing condition including either an increase in frequency and/or intensity of the condition.
- New conditions detected or diagnosed after study medication administration even though it may have been present before the start of the study.
- Signs, symptoms, or the clinical sequelae of a suspected drug-drug interaction.
- Signs, symptoms, or the clinical sequelae of a suspected overdose of either study medication or a concomitant medication. Overdose per se will not be reported as an AE/SAE unless it is an intentional overdose taken with possible suicidal/self-harming intent. Such overdoses should be reported regardless of sequelae.
- "Lack of efficacy" or "failure of expected pharmacological action" per se will not be reported as an AE or SAE. Such instances will be captured in the efficacy assessments. However, the signs, symptoms, and/or clinical sequelae resulting from lack of efficacy will be reported as AE or SAE if they fulfill the definition of an AE or SAE.

Events NOT Meeting the AE Definition

- Any clinically significant abnormal laboratory findings or other abnormal safety assessments which are associated with the underlying disease, unless judged by the Investigator to be more severe than expected for the participant's condition.

- The disease/disorder being studied or expected progression, signs, or symptoms of the disease/disorder being studied, unless more severe than expected for the study participant’s condition.
- Medical or surgical procedure (eg, endoscopy, appendectomy): the condition that leads to the procedure is the AE.
- Situations in which an untoward medical occurrence did not occur (social and/or convenience admission to a hospital).
- Anticipated day-to-day fluctuations of pre-existing disease(s) or condition(s) present or detected at the start of the study that do not worsen.

10.3.2 Definition of SAE

If an event is not an AE per definition above, then it cannot be an SAE even if serious conditions are met (eg, hospitalization for signs/symptoms of the disease under study, death due to progression of disease).

An SAE is defined as any untoward medical occurrence that, at any dose:

a. Results in death

b. Is life-threatening

The term 'life-threatening' in the definition of 'serious' refers to an event in which the participant was at risk of death at the time of the event. It does not refer to an event, which hypothetically might have caused death, if it were more severe.

c. Requires inpatient hospitalization or prolongation of existing hospitalization

In general, hospitalization signifies that the participant has been detained (usually involving at least an overnight stay) at the hospital or emergency ward for observation and/or treatment that would not have been appropriate in the physician’s office or outpatient setting. Complications that occur during hospitalization are AEs. If a complication prolongs hospitalization or fulfills any other serious criteria, the event is serious. When in doubt as to whether “hospitalization” occurred or was necessary, the AE should be considered serious.

Hospitalization for elective treatment of a pre-existing condition that did not worsen from Baseline is not considered an AE.

d. Results in persistent disability/incapacity

- The term disability means a substantial disruption of a person’s ability to conduct normal life functions.
- This definition is not intended to include experiences of relatively minor medical significance such as uncomplicated headache, nausea, vomiting, diarrhea, influenza, and accidental trauma (eg, sprained ankle) which may interfere with or prevent everyday life functions but do not constitute a substantial disruption.

e. Is a congenital anomaly/birth defect

f. Important medical events:

- Medical or scientific judgment should be exercised in deciding whether SAE reporting is appropriate in other situations such as important medical events that may not be immediately life-threatening or result in death or hospitalization but may jeopardize the participant or may require medical or surgical intervention to prevent one of the other outcomes listed in the above definition. These events should usually be considered serious.

Examples of such events include, but are not limited to, potential Hy's law, invasive or malignant cancers, intensive treatment in an emergency room or at home for allergic bronchospasm, blood dyscrasias or convulsions that do not result in hospitalization, or development of drug dependency or drug abuse.

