10.2.2 AE summaries

Summary tables with the number, percentage of study participants and frequency of TEAEs will be provided by treatment group and RLZ total. Additional details are as follows:

1. Overview of TEAEs will include following categories: any TEAEs, serious TEAEs, participant discontinuation due to TEAEs, permanent withdrawal of IMP due to TEAEs, temporary withdrawal of IMP due to TEAEs, treatment-related TEAEs, severe TEAEs, TEAEs leading to death, all deaths (AEs leading to death).
2. Incidence of TEAEs will be summarized by SOC, HLT and PT for:
 - Any TEAEs
 - TEAEs during Treatment Period
 - Severe TEAEs
 - Any TEAEs by maximum intensity (mild, moderate and severe)
 - Any TEAEs by relationship
 - Any TEAEs relative to ADA status
 - Any TEAE by Risk Difference $\geq 5\%$ (by decreasing frequency of Risk Difference)
 - Non-serious TEAEs above reporting threshold of 5% of study participants
 - Fatal TEAEs
 - Fatal TEAEs by relationship
 - Serious TEAEs
 - Serious TEAEs by relationship
 - Participant discontinuation due to TEAEs
 - TEAEs leading to permanent withdrawal of IMP
 - TEAEs leading to temporary withdrawal of IMP
 - Treatment-emergent AESM
 - Treatment-emergent AESI
3. Incidence of TEAEs will be summarized by PT for:
 - Any TEAEs by decreasing frequency of PT

AESMs include severe headache, severe GI disorders (i.e., abdominal pain, diarrhea, vomiting), and opportunistic infection.

AESIs are the cases of potential Hy's Law (see [Section 10.3.1](#)).

AESMs and AESIs will be identified based on the assessment by the Investigator as recorded in the CRF. An AE will be counted as an AESM if there is a 'yes' response to the question "Adverse event of Special Monitoring?" and 'no' otherwise. An AE will be counted as an AESI

if there is a ‘yes’ response to the question “Adverse Event of Special Interest?” and ‘no’ otherwise.

When applicable adverse event summaries will be ordered by alphabetical SOC, alphabetical HLT within SOC and decreasing frequency of PT in the rozanolixizumab total column for tables.

Listings of all TEAEs, all non-serious TEAEs, serious TEAEs, permanent withdrawal of IMP due to AEs, study participant discontinuation from study due to AEs, AEs leading to death, AESIs, AESMs will be presented by treatment group and study participants.

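### A death judged to be expected progression of myasthenia gravis need not be an AE, and the SAP counts all deaths only through AEs, so such a death would be missing from the all-deaths row and the death listing.

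*Protocol*

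**What the plan says.** **Protocol 10.3.1** sorts MG events in two directions.

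- Among events that are not AEs it places the disease itself and its "expected progression, signs, or symptoms of the disease/disorder being studied, unless more severe than expected" for that participant.
- Among events that are AEs it places "Exacerbation of a chronic or intermittent pre-existing condition including either an increase in frequency and/or intensity of the condition".
- On lack of efficacy, it says that the resulting "clinical sequelae resulting from lack of efficacy will be reported as AE or SAE if they fulfill the definition of an AE or SAE".

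**Protocol 10.3.2** opens with a condition, that the event is not an AE as defined in 10.3.1. Where that condition is met, "it cannot be an SAE even if serious conditions are met (eg, hospitalization for signs/symptoms of the disease under study, death due to progression" of the disease.

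**SAP 10.2.2** ends its list of overview categories with "TEAEs leading to death, all deaths (AEs leading to death" and closes the bracket there. SAP 11.1 uses the same category for the Japan overview. The only death listing in SAP 10.2.2 is of AEs leading to death. In SAP 5.1, fatal outcomes are named only within the summary of discontinuations due to AEs.

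**The concern.** The overview has one row for TEAEs leading to death and another for all deaths, so a reader will take the second as complete. It goes beyond the treatment-emergent window, but it still starts from AE records. Protocol 10.3.2 meanwhile names death from disease progression as something that can fall outside AE and SAE reporting. Taken together, the two documents allow a death to occur on study and appear in neither the death count nor the death listing.

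This matters because the protocol describes MG as sometimes life-threatening. It enrols MGFA Class II to IVa participants already being considered for IVIg or PEX, has a placebo arm, and follows participants for 8 weeks off drug. A death count by arm is a basic safety result. Here its completeness would rest on the judgement of investigators at about 135 sites, using a term (expected) that the protocol does not define for this disease.

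**Working it through.** The plan states no figure to reproduce, and the point turns on definitions. The check is to follow one fatal MG event through the planned outputs under each of the two classifications that Protocol 10.3.1 allows.

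| Step or output | Judged an exacerbation, or worse than expected | Judged expected progression |
|---|---|---|
| AE (Protocol 10.3.1) | Yes | No |
| SAE (Protocol 10.3.2) | Yes | No |
| Fatal and serious TEAE tables (SAP 10.2.2) | Yes, if onset is within the TEAE window | No |
| All-deaths row, main overview (SAP 10.2.2) | Yes | No |
| All-deaths row, Japan overview (SAP 11.1), Japanese participants | Yes | No |
| Listing of AEs leading to death (SAP 10.2.2) | Yes | No |
| Fatal categories under discontinuation due to AEs (SAP 5.1) | Yes | No |
| Disposition summary and listings (SAP 5.1) | Yes | Yes, as a discontinuation; the SAP names no death reason |

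The same event gives two different death counts, and only the investigator's view of it differs.

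Next, whether another planned output supplies the missing count:

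- Rescue use and time to first rescue (SAP 8.4.1, 8.4.2) record IVIg and PEX, not death or hospitalisation.
- MG-ADL, QMG and MG-C continue to Visit 14, and MGFA class is recorded at Visits 10 and 14. These show worsening in participants who are assessed.
- Protocol 10.3.3 asks for any post-mortem findings to go to the sponsor, but no planned table uses them.
- Protocol 8.10 states that resource use is not measured, so hospital stays are not collected by that route.
- The IDMC data lists in SAP 4.4.2.1 and 4.4.2.2 include adverse events and the three MG scores, with no separate item for deaths from any cause.

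None of these counts deaths independently of AE status.

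On size, only a per-event statement is possible. SAP 2.4 plans 30 participants per arm in Stage 1 and 30 to 50 per continuing arm in Stage 2, so a continuing arm has 30 + 30 = 60 to 30 + 50 = 80. One omitted death would understate that arm's mortality by 1/80 = 1.25 to 1/60 = 1.7 percentage points.

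**The case against.** The strongest reply is that Appendix 3 contains no blanket exclusion. A reader who starts from the examples in 10.3.2 might infer that an MG hospitalisation or death can never be an SAE. The text does not support that. The rule applies only to events that are not AEs. Section 10.3.1 brings in events worse than expected, includes exacerbations of pre-existing conditions, and excludes day-to-day fluctuation only where there is no worsening. Exclusion criterion 17a also removes participants with crisis or impending crisis at Visits 1 and 2, so a crisis arising later would most naturally be an AE and, if it led to hospitalisation, an SAE. This stands.

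Two further replies also stand. The lack-of-efficacy text does not state an opposite rule: it depends on the AE or SAE definition being met, so for MG symptoms it returns to the same question. And it would be wrong to infer that no other output captures MG worsening, since rescue use, the MG scores, MGFA class, concomitant procedures and disposition listings each give a partial view.

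A reader might also infer that the IDMC would not learn of such a death. That cannot be shown. SAP 4.4.2 says the IDMC data include everything specified in the Charter, which is not among the documents.

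None of these replies reaches the death count. Partial visibility of worsening does not make the all-deaths row complete, and Protocol 10.3.2 itself gives death due to progression as an example of what can fall outside.

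**Conclusion.** The point holds in a limited form. Protocol 10.3.1 and 10.3.2 allow an MG hospitalisation or death judged expected progression to be a non-AE and so a non-SAE, while the exacerbation item in 10.3.1 points the other way. Because the SAP defines all deaths through AEs, a death classified in that way would be missing from the all-deaths row in both overviews and from the death listing.

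This rests on one assumption: that at least one investigator applies the expected-progression exclusion to a fatal event, which the protocol's own example invites. If no death is classified in that way, the count is unaffected.

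It is tempting to turn an assumed rate of serious MG events into a number at risk of omission. The documents give no rate, and only events judged no worse than expected could be lost, so no such number is supported. Nor do the documents settle whether every serious MG worsening should be an SAE. That is a debatable reporting choice, and this point does not depend on it.

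**What to change.** 1. In SAP 10.2.2 and 11.1, count and list deaths from any cause by arm and by period (Treatment, Observation), regardless of AE status, and state the date up to which deaths are counted. Keep AEs leading to death as a separate row.
2. Name the source. The study termination page is a candidate, since both documents refer to it. They do not say that it records death, so this needs checking and a field added if it is absent.
3. Add the all-cause death count to the IDMC outputs in SAP 4.4.2.1 and 4.4.2.2, and check it against the Charter.
4. Reconcile the exacerbation and expected-progression items in Protocol 10.3.1 with the examples in 10.3.2, so that sites classify fatal or hospitalised MG worsening in the same way.

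The cost is one table row and one listing, possibly one data field, and a wording change in Appendix 3 with a note to sites. Treatment, visits and the efficacy analysis are unaffected.

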10.3.3 Recording and Follow-Up of AE and/or SAE

AE and SAE Recording

- When an AE/SAE occurs, it is the responsibility of the Investigator to review all documentation (eg, hospital progress notes, laboratory reports, and diagnostics reports) related to the event.
- The Investigator will then record all relevant AE/SAE information in the eCRF.
- It is **not** acceptable for the Investigator to send photocopies of the participant's medical records to UCB in lieu of completion of the UCB AE/SAE eCRF page.
- There may be instances when copies of medical records for certain cases are requested by UCB. In this case, all participant identifiers, with the exception of the participant number, will be redacted on the copies of the medical records before submission to UCB.
- The Investigator will attempt to establish a diagnosis of the event based on signs, symptoms, and/or other clinical information. Whenever possible, the diagnosis (not the individual signs/symptoms) will be documented as the AE/SAE.

Assessment of Intensity

The Investigator will make an assessment of intensity for each AE and SAE reported during the study and assign it to 1 of the following categories:

- **Mild:** An event that is easily tolerated by the participant, causing minimal discomfort and not interfering with everyday activities.
- **Moderate:** An event that causes sufficient discomfort and interferes with normal everyday activities.

- Severe: An event that prevents normal everyday activities. An AE that is assessed as severe should not be confused with an SAE. Severe is a category utilized for rating the intensity of an event; and both AEs and SAEs can be assessed as severe.
- An event is defined as ‘serious’ when it meets at least 1 of the predefined outcomes as described in the definition of an SAE, NOT when it is rated as severe (eg, a severe AE may be either serious or not serious, depending on whether these criteria are also met).

The National Cancer Institute Common Terminology Criteria for Adverse Events (NCI-CTCAE) should be used as a supportive standardization instrument to evaluate AEs and SAEs but the final intensity grading by the Investigator must be mild, moderate, or severe.

Assessment of Causality

- The Investigator is obligated to assess the relationship between study medication and each occurrence of each AE/SAE.
- A "reasonable possibility" of a relationship conveys that there are facts, evidence, and/or arguments to suggest a causal relationship, rather than a relationship cannot be ruled out.
- The Investigator will use clinical judgment to determine the relationship.
- Alternative causes, such as underlying disease(s), concomitant therapy, and other risk factors, as well as the temporal relationship of the event to study medication administration will be considered and investigated.
- The Investigator will also consult the Investigator’s Brochure (IB) in his/her assessment.
- For each AE/SAE, the Investigator **must** document in the medical notes that he/she has reviewed the AE/SAE and has provided an assessment of causality.
- There may be situations in which an SAE has occurred and the Investigator has minimal information to include in the initial report to UCB. However, **it is very important that the Investigator always make an assessment of causality for every event before the initial transmission of the SAE data to UCB.**
- The Investigator may change his/her opinion of causality in light of follow-up information and send an SAE follow-up report with the updated causality assessment.
- The causality assessment is one of the criteria used when determining regulatory reporting requirements.

Follow-up of AEs and SAEs

- The Investigator is obligated to perform or arrange for the conduct of supplemental measurements and/or evaluations as medically indicated or as requested by UCB to elucidate the nature and/or causality of the AE or SAE as fully as possible. This may include additional laboratory tests or investigations, histopathological examinations, or consultation with other health care professionals.
- An AE should be followed until it has resolved, has a stable sequelae, the Investigator determines that it is no longer clinically significant, or the participant is lost to follow-up. This follow-up requirement applies to AEs, SAEs, and AEs of special interest.
- If a participant dies during participation in the study or during a recognized follow-up period, the Investigator will provide UCB with a copy of any post-mortem findings including histopathology.
- New or updated information will be recorded in the originally completed CRF.
- The Investigator will submit any updated SAE data to UCB within 24 hours of receipt of the information.

